management. Without unblinding, it will be evident that all subjects will have received 40mg/kg Phenobarbital and 60mg/kg of LEV at this stage.

[figure not shown]

Figure 3 Predicted blood levels at 40 mg/kg and 60 mg/kg loads with 10 mg/kg 8 hourly maintenance

Clinical monitoring and specific laboratory data will be collected at standardized times following study drug administration to determine the pharmacokinetics and safety of LEV on 12 subjects at the 40 mg/kg dose and 12 at the 60 mg/kg dose (see Table 2). The PK studies will be performed only at the San Diego and Auckland sites. Investigators will remain blinded to PB level.

Table 2	CBC diff	Chem Panel, LFTs	LEV level	Phenobarbital Level
Baseline	X	X	X	X
1 hour			X	X
24 hours			X	X
48 hours	X	X	X	X

Study Inclusion and Exclusion criteria: To be eligible for recruitment, subjects will be term infants with corrected gestational age between 36 and 44 weeks, and weight of at least 2.2 kg. Subjects will be excluded if they have received anticonvulsants within 24 hours of enrolling in the study, if serum creatinine is

greater than 1.6 mg/dL or if seizures are due to correctable metabolic abnormalities (i.e.hypoglycaemia, hypocalcemia, hyponatremia). Subjects in whom death seems imminent, as assessed by the neonatologist, will also be excluded from the study.

Recruitment: There are 2 groups of babies from which subjects may be recruited-

1. A prospective group, where it can be anticipated that seizures are at high risk of occurring, for example in neonates with HIE. Consent will be obtained prospectively and continuous EEG monitoring will commence.
2. Acutely presenting group, neonates that present with symptoms indicative of or suggestive of seizures. It is recognised that it will not be possible to recruit all patients in this acutely presenting group. Efforts to obtain consent can not be allowed to delay management. However, in many cases there will be opportunity to ethically recruit and consent subjects without delaying care. For example, in cases where clinical seizures are brief and have stopped spontaneously, and in cases where there is suspicion of seizure activity but EEG confirmation is needed before AEDs are indicated.

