Feasibility data: We will record the times of the following events: subject admission to NICU, contact of study staff by treating physicians, subject enrolment, initiation of EEG monitoring, first recognized seizure, and time of study drug administration. Record will be made of whether seizure is first identified by Corticare staff or by onsite study investigator. Record will be systematically collected from each monitored subject of any difficulties with functioning of the remote continuous monitoring infrastructure. All data will be referenced to date/time of birth so that precise age in hours can be determined for age at enrolment, timing of seizures, administration of study drug, and administration of other treatments given to treat seizures.

Safety data: Continuous monitoring of vital signs will occur as part of routine neonatal intensive care. Vital signs will be recorded at baseline, and at 15 minutes after each drug infusion commences. Documentation of presence or absence of adverse event occurring during each treatment phase will be made. Blood tests of haematological indices, electrolytes, glucose, renal function and liver enzymes will be tested and recorded at baseline, at 24 hours and at 48 hours as part of safety and adverse events monitoring.

Pharmacokinetic data: For subjects at the 3 San Diego sites serum LEV levels will be drawn at baseline, 1 hour after starting the treatment, at 24 and 48 hours.

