Data that will be collected specifically for the purposes of this trial will include clinical data regarding the subjects' medical history and hospital course including clinical characteristics such as weight, medications administered, blood pressure measurements, and fluid input/output. Most clinical data will be obtained from the subjects' medical records, but there may be some data obtained by interviewing the parent(s).

Much of the laboratory data that will be recorded in the database will be laboratory data obtained in newborns as part of standard clinical care of newborns with seizures, such as serum blood gas measurements, serum electrolytes, levels of AEDs administered and liver function tests. Some laboratory tests such as albumin and serum bicarbonate may not be collected at both time points for standard care for some subjects and thus will be obtained for purposes of the trial. Serum LEV levels will be collected only for purposes of this trial.

EEG data will be read and used for clinical purposes at each site with the assistance of the remote centralized continuous monitoring system. For the purposes of the study itself EEG data collected at each site will be de-identified before analysis by the study neurophysiologists who will be blinded to the subjects' group assignment or demographic information.

Study staff at each site will have access to individually identifiable information about newborns enrolled at that site. Data will be collected by each site's study investigators and the research coordinator and recorded onto case report forms (CRFs) by the research coordinator, and data from the CRFs will subsequently be entered into the database by the research coordinator. The CRFs and the electronic database will only have de-identified information to preserve confidentiality of patients' protected health information. Files that link the study identification number for each subject to the subject's personal information (such as name, medical

record number, parents' names) will be kept at each site and accessible only by the site PI and research coordinator.

10. RECRUITMENT AND SCREENING:

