As described above LEV is a very safe drug with a wide therapeutic range. However, any adverse drug reaction is possible. Careful monitoring for adverse drug reactions will be maintained throughout the treatment period. Neonates will be monitored continuously during the study period for heart rate, respiratory rate and blood pressure. Serum chemistries and CBC will be performed at baseline and after 48 hours of treatment with study drug. Daily physical examinations will be performed while in-house and record made of the occurrence of hypotonia, sedation, poor feeding, irritability or infection. Since all subjects will be closely monitored by clinical, laboratory and EEG data, it is expected that adverse events can be anticipated and managed rapidly and effectively by the treating clinicians.

If there are serious adverse events, these events will be reported to the IRB within 24 hours of knowledge of the event, and will be reported to the DSMB in the timeframe that they require.

Mechanism proposed to minimize the patient's potential risks involving blood drawing

Blood drawing will be done by clinical staff who are trained and experienced in drawing blood from newborns. A clinically indicated indwelling arterial or venous catheter will be present in most study subjects, so that in most cases there will be no discomfort to the newborns from needle sticks for research-only blood draws. Sterile techniques will be used at all times to minimize the chance of infection, thereby minimizing potential risks related to the collection of blood samples. It is possible that in some subjects indwelling arterial or venous catheter access will not be maintained throughout the study period and may require additional venipunctures or heel stick blood draws. All efforts will be made to reduce infants discomfort by warming the heel adequately prior to blood draw, administering oral glucose during blood draw and feeding infant after blood draw.

Mechanism proposed to minimize patients' risk of time delay to effective AED therapy

Our study design ensures rapid escalation to treatment with Phenobarbital in subjects who do not respond to LEV. Additionally, because our study will utilize real time monitoring of continuous EEG recordings leading to more rapid detection and treatment of electrographic seizures than is normally standard of care, our study subjects will receive AED treatment in a shorter time frame than is usual. LEV has good efficacy in other

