populations, including in populations experiencing refractory status epilepticus. In neonates there are accumulating reports of its efficacy in cases where seizures are refractory to multiple other agents. Our preliminary analysis of efficacy when LEV is used as a second line agent suggests efficacy similar to that of Phenobarbital and phenytoin when used as second line agents. Therefore we believe that the risk that the overall risk to patients is low in this regard

Specific Measures to reduce potential risks listed in (13)

1. Measures to reduce pain from venipunctures

For the first days of the study all patients will have indwelling vessel catheter in place as part of their routine care. This will render blood sampling painless and free of any risk beyond that usually associated with the care of a critically ill newborn. Blood sampling towards the end of the 1-week treatment period may require additional venipunctures or heel stick blood draws. All efforts will be made to reduce infants discomfort by warming the heel adequately prior to blood draw, administering oral glucose during blood draw and feeding infant after blood draw.

2. Measures to reduce risk secondary to blood loss from venipunctures

The total blood drawn over 2 days for the study will be 44 to 5 ml (4 x 0.5 ml specimens for levetiracetam levels, and at the same lab draw as the last levetiracetam level an additional 1.0 ml for chemistry CBC and phenobarbital level). By excluding infants with birth weights less than 2440g we will be able to ensure that this is a safe percentage ($\leq 3\%$) of the infants total blood volume.

3. Adverse drug reaction

As above levetiracetam is apparently a very safe drug with a wide therapeutic range. Adverse drug reactions to orally administered levetiracetam in adults and older children have been exceedingly rare. Use of the IV formulation in animal studies and a PK study in adults has so far not been associated with serious adverse drug reactions. However, any adverse drug reaction is possible including serious anaphylactic reaction and death. Careful monitoring for adverse drug reactions will be maintained throughout the treatment period:

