Levetiracetam has been well tolerated in other age groups and found to be without significant risks. Adverse events have mainly consisted of CNS effects such as somnolence, asthenia, coordination difficulty and behavioral symptoms. Other than 2 cases of reversible thrombocytopenia associated with levetiracetam use, no unexpected toxicities or serious laboratory abnormalities have been reported.

Neonates will be monitored continuously during the study period for heart rate, respiratory rate and blood pressure.

Serum chemistries, and CBC will be performed at baseline and at end of treatment.

Daily physical examinations will be performed while in-house and record made of the occurrence of hypotonia, sedation, poor feeding, irritability or infection.

Following the last dose of study drug, a phone review of the same symptoms will be conducted every 3 days and a visit and physical examination will be conducted one week after the last dose of study drug. A home visit or clinic visit can be conducted if the subject is discharged.

4. Mechanism proposed to minimize patients' risk of time delay to effective AED therapy

Our study design ensures rapid escalation to treatment with Phenobarbital in subjects who do not respond to LEV. Additionally, because our study will utilize real time monitoring of continuous EEG recordings leading to more rapid detection and treatment of electrographic seizures than is normally standard of care, our study

subjects will receive AED treatment in a shorter time frame than is usual. LEV has good efficacy in other populations, including in populations experiencing refractory status epilepticus. In neonates there are accumulating reports of its efficacy in cases where seizures are refractory to multiple other agents. Our preliminary analysis of efficacy when LEV is used as a second line agent suggests efficacy similar to that of Phenobarbital and phenytoin when used as second line agents. Therefore we believe that the overall risk to patients is lower than the usual clinical care risk when using our treatment protocol. The continuous EEG monitoring that will be used for the study will mean that these determinations of the efficacy of medications will be possible sooner than is possible with routine management.

5. Measures to safeguard confidentiality of data.

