### 4.4 Safety Outcomes

- Rate of Adverse Events (AEs)
- Rate of Serious Adverse Events (SAE)
- Discontinuation Rate
- Laboratory data
- PK analysis of LEV

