## 7.5 Analysis of Safety Outcomes

Adverse Event and Serious Adverse Events will be tabulated by randomization group and by drugs received, respectively. Details including seriousness, intensity, causality, withdrawal due to event and outcome will be summarized by frequencies and percentages by randomization group and by drugs received. Fisher's exact tests will be used to compare rates of adverse events, serious adverse events, study discontinuation and deaths between randomization group and by drugs received, respectively.

Findings will be tabulated by randomization group overall and for findings marked as AE and SAE, respectively.

Safety Labs (using DAIDS guidelines) will be presented with shift tables (hour 48 vs baseline) by randomization group and by drugs received, respectively.

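### The protocol gives three different safety-lab schedules; SAP 7.5 follows one (baseline and hour 48) without saying so, so any 24-hour or end-of-treatment labs have no planned shift analysis

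*SAP*

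**What the plan says.** SAP 4.4 lists "Laboratory data" among the safety outcomes and gives no time points. SAP 7.5 supplies the only analysis of them: "Safety Labs (using DAIDS guidelines) will be presented with shift tables (hour 48 vs baseline) by randomization group and by drugs received". No other SAP section analyses safety labs.

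The protocol describes the timing in four places:

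- Section 8, study design summary, says that "Clinical monitoring and specific laboratory data will be collected at standardized times following study drug administration" and points to Table 2. The table marks blood count and chemistry with liver tests at baseline and 48 hours. Its 1-hour and 24-hour rows carry drug levels only.
- Section 14, on limiting adverse drug reactions to LEV: "Serum chemistries and CBC will be performed at baseline and after 48 hours of treatment with study drug".
- Section 8, safety data: the haematology, electrolyte, glucose, renal and liver tests "will be tested and recorded at baseline, at 24 hours and at 48 hours as part of safety and adverse events monitoring".
- Section 14, specific measures, item 3: "Serum chemistries, and CBC will be performed at baseline and at end of treatment".

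Treatment length also varies. Section 4 says 5 days, section 8 says maintenance runs for 5 days or more, and sections 13 and 14 mention a one-week treatment period.

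**The concern.** Aim 4 is the safety of high-dose LEV. Section 13 names reversible thrombocytopenia and a possible case of liver failure, both of which laboratory tests would detect. The pilot study in section 7 took safety labs at baseline, between 48 and 72 hours, and on completing 7 days.

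A reader who compares the SAP with the section 8 safety-data paragraph, or with item 3 of section 14, finds lab values that the protocol says are obtained and that the SAP never tabulates. A grade shift present at 24 hours and gone by 48, or one that first appears after 48 hours, would not enter the shift tables. What is at stake is how much of the dosing period a statement about laboratory safety can cover.

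**Working it through.** The plan states no figure on this point, so there is none to reproduce. The check compares the passages and then works out the share of dosing covered.

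**Step 1. Each protocol schedule against SAP 7.5**

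| Protocol source | Post-baseline safety labs | In the SAP shift table | Without a planned shift analysis |
|---|---|---|---|
| Section 8 Table 2; section 14, limiting reactions to LEV | 48 h | 48 h | none |
| Section 8, safety data | 24 h, 48 h | 48 h | 24 h |
| Section 14, specific measures, item 3 | end of treatment | none | end of treatment |

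No passage lists 24 hours, 48 hours and end of treatment together.

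**Step 2. Other passages that bear on the schedule**

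- Section 9: "Some laboratory tests such as albumin and serum bicarbonate may not be collected at both time points for standard care". This implies two time points. It fits the first or third row of the table, but not the second.
- Section 14, specific measures, item 2, itemises the blood drawn as four LEV samples and, "at the same lab draw as the last levetiracetam level an additional 1.0 ml for chemistry CBC and phenobarbital level". LEV levels are taken at baseline, 1, 24 and 48 hours, so the last is at 48 hours. The items sum to 4 × 0.5 + 1.0 = 3.0 ml, with no safety draw at 24 hours or at end of treatment. This fits the first row.
- The sentence that introduces Table 2 refers to 12 infants at each of two dose levels, 24 in all, against 100 planned treated infants. Table 2 alone therefore does not settle the schedule for everyone.

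**Step 3. Share of planned dosing up to the last analysed lab**

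Share covered = 48 / T, where T is the planned treatment time in hours.

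- 5 days (section 4): T = 5 × 24 = 120. Covered: 48/120 = 40%. After hour 48: 72/120 = 60%.
- Any course longer than 5 days makes T larger and the share smaller, so 40% is a maximum for an infant who completes the course.
- One-week wording: T = 168. Covered: 48/168 = 29%. After hour 48: 120/168 = 71%.
- In doses, assuming 8-hourly maintenance at 8, 16, ..., 120 h: 15 doses, of which those from 56 to 120 h, (120 − 56)/8 + 1 = 9, come after hour 48. That is again 60%.

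**The case against.** The best defence is that the SAP analyses exactly what the protocol's own lab table schedules. On that version every scheduled safety lab is used, and the gap after hour 48 lies in data collection, not in the SAP. The end-of-treatment line is also weak evidence. It stands close to a one-week treatment period and a 2440 g weight limit, both of which match the pilot study and not this trial's 5 days and 2200 g, so it may be carried-over text (an inference). Clinically important abnormalities at other times can still reach the adverse event tables. A worst-grade summary, for its part, rises with the number of samples per infant.

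Much of this stands, and it rules out three stronger readings that a reader might infer:

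- *The SAP discards two of three scheduled post-baseline values.* This merges schedules that are alternatives; no passage sets out all three visits.
- *The sickest infants drop out of the table.* The documents do not show it. Section 13 expects most infants to have these tests as standard care, section 14 expects most to have a catheter in place, deaths are compared separately in SAP 7.5, and the SAP does not say that infants without an hour-48 value are excluded.
- *The number of missed abnormalities can be estimated.* That needs a per-visit rate and the correlation between visits, and the documents give neither.

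The defence does not remove the contradiction, nor the SAP's silence on which schedule it follows. The adverse event tables are only a partial substitute: they depend on a decision to report, and section 14 lists abnormal labs associated with organ failure as expected events. DAIDS grading of every scheduled value does not depend on that decision.

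**Conclusion.** The point holds as one of consistency and completeness. The protocol has three incompatible safety-lab schedules, and the SAP adopts one of them tacitly. If labs were taken as either of the other two describes, those values have no planned shift analysis. If not, the planned laboratory evidence for Aim 4 ends at hour 48, with at least 72 of 120 hours (60%) of a completed 5-day course still to come.

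The 40% and 60% figures assume that the infant completes planned treatment. They measure dosing time, not toxicity missed. The documents do not say which labs were actually drawn or entered. This should be corrected, but it does not affect the efficacy analyses.

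**What to change.** 1. Reconcile Table 2 and the matching section 14 paragraph with the section 8 safety-data paragraph and with section 14, specific measures, item 3. State which safety labs were scheduled and which were collected. Section 11 already refers to recruitment having closed, so the study records should answer this.
2. In SAP 7.5, name the schedule being followed and keep the hour-48 shift table.
3. For every other scheduled safety-lab time point actually collected, add a shift table from baseline. Add one table of baseline against worst post-baseline DAIDS grade over the scheduled draws. Present both by randomised group and by drugs received, with the number of infants sampled per arm and time point.
4. If no other scheduled labs were collected, say in the safety conclusions that planned laboratory data stop at 48 hours of a 5-day course.

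The cost is one or two further tables, with no new blood samples and no change to patient care. The worst-grade table remains sensitive to how often each infant was sampled. Limiting it to scheduled draws and printing the sample counts largely contains that problem but does not remove it.

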## 7.6 Pharmacokinetic Analysis

**These analyses will be performed by [name] at UC San Diego. The below analysis plan is a preliminary plan as stated in the study research plan, a more detailed analysis plan will be provided by [name] at the time of analysis.**

The actual individual concentration data, collection times and dosing histories will be used to create graphs of plasma LEV concentration vs. time for each infant. Median plasma drug concentration vs. time curves will also be generated. Summary statistics (i.e., n, mean, standard deviation, median, minimum, maximum, and coefficient of variation) will be calculated for

[figure not shown]
CONFIDENTIALITY STATEMENT: This report from the USC Alzheimer's Therapeutic Research Institute (ATRI) is for the sole use of the intended recipient(s) and contains confidential and privileged information. Any unauthorized review, use, disclosure, copying or distribution is strictly prohibited.

plasma concentrations for each time point and each dose level. LEV population pharmacokinetic parameters will be determined using the computer program NONMEM (ver. 6 or later). The data will be nested with existing raw infant LEV pharmacokinetic data generated in the preliminary LEV study. Assuming linear pharmacokinetics as suggested by our current pharmacokinetic data, studying 12 subjects at each dosage level will result in 90% confidence intervals for the pharmacokinetic parameters (CL, V and  $t_{1/2}$ ) of  $\pm 15\%$ . The 90% confidence intervals for the exposure parameters ( $C_{max}$ , AUC) will be approximately  $\pm 20\%$ . The pharmacokinetics will be modeled recognizing the two stages of a nonlinear hierarchical model development. The first stage introduces the structural model (e.g. one compartment open model), the population parameters, individual effects and the within-patient variation. The second portion of the model development recognizes that variation between patients in the pharmacokinetic parameters exists and will attempt to determine covariates that may identify different pharmacokinetic subpopulations. A one-compartment model with first order elimination will be utilized. Alternative structural models will be explored if indicated by the data. The impact of clinical factors and demographic factors (including weight, sex, age, race, serum creatinine, hypothermia and dosing regimen) will be assessed as fixed effects in the model. Nested models will be compared graphically and with a likelihood ratio test.

